**Table 1.3. 13: Summary statistics for time taken for each screening test to be completed**

Screening test	Statistics	Length of procedure (minutes)	Length of procedure and set up (minutes)
MRI	N	xxx	xxx
	Mean (SD)	xx.xx (xx.xx)	xx.xx (xx.xx)
	Median (IQR)	xx.xx (xx.xx)	xx.xx (xx.xx)
	Missing from eCRF – n (%)	xx (xx%)	xx (xx%)
Ultrasound	N	xxx	xxx
	Mean (SD)	xx.xx (xx.xx)	xx.xx (xx.xx)
	Median (IQR)	xx.xx (xx.xx)	xx.xx (xx.xx)
	Missing from eCRF – n (%)	xx (xx%)	xx (xx%)
PSA	N	xxx	xxx
	Mean (SD)	xx.xx (xx.xx)	xx.xx (xx.xx)
	Median (IQR)	xx.xx (xx.xx)	xx.xx (xx.xx)
	Missing from eCRF – n (%)	xx (xx%)	xx (xx%)

**Table 1.3. 14: Proportion of participants who undergo a repeat screening assessment for MRI, Ultrasound and/or PSA**

Repeat screening assessments	MRI	Ultrasound	PSA	Total 
Proportion – n (%)	xxx (xx%)	xxx (xx%)	xxx (xx%)	xxx (xx%)
95% confidence interval	x.xx to x.xx	x.xx to x.xx	x.xx to x.xx	x.xx to x.xx

Total number of participants who underwent at least one repeat screening assessment

**Table 1.3. 15: Proportion of incidental findings for MRI and Ultrasound screening tests**

Type of Incidental Finding	MRI	Ultrasound
None	xx (xx%)	xx (xx%)
Bladder Tumour	xx (xx%)	xx (xx%)
Rectal Tumour	xx (xx%)	xx (xx%)
Other (please specify):	xxx (xx%)	xxx (xx%)
...	xx (xx%)	xx (xx%)
...	xx (xx%)	xx (xx%)
...	xx (xx%)	xx (xx%)

#### 11.6.4. Other End Point

**Table 1.4. 1: Rates of biopsy related adverse events (infectious complications, urinary retention, and haematuria requiring admission)**

Biopsy related adverse events (subjects*)	Proportion – n (%)
---	--------------------

Imperial Clinical Trials Unit	STATISTICAL ANALYSIS PLAN	PROSTAGRAM
-------------------------------	---------------------------	------------

Infectious complications:	xxx (xx%)
Presence	xxx (xx%)
Experienced complications	xxx (xx%)
Healthcare contact	xxx (xx%)
Urinary retention:	xxx (xx%)
Presence	xxx (xx%)
Experienced complications	xxx (xx%)
Healthcare contact	xxx (xx%)
Haematuria requiring admission:	xxx (xx%)
Presence	xxx (xx%)
Experienced complications	xxx (xx%)
Healthcare contact	xxx (xx%)
Total	xxx (xx%)

\*Table note: Where subjects have more than one AE the highest relationship has been used

#### 11.6.5. Safety Analysis

**Table 1.5. 1: Listing of all adverse events**

Subject ID	Diagnosis	Onset Date	Recovery Date	Duration (days)	Relationship	Severity	Expectedness	Serious

**Table 1.5. 2: Incidence of expected adverse events (see Appendix 3)**

Event class	Total - n (%)
Expected study-related adverse events:	xx (xx%)
Haematomas and ecchymoses around venepuncture site	xx (xx%)
Minor discomfort	xx (xx%)
Infection	xx (xx%)
Expected adverse events associated with MRI:	xx (xx%)
Claustrophobia	xx (xx%)
Anxiety/Stress	xx (xx%)
Discomfort	xx (xx%)
Expected adverse events associated with Prostate M-P US:	xx (xx%)
Minimal rectal discomfort during the procedure	xx (xx%)
Expected adverse events associated with Prostate Biopsy:	xx (xx%)
	xx (xx%)

Imperial Clinical Trials Unit	STATISTICAL ANALYSIS PLAN	PROSTAGRAM
-------------------------------	---------------------------	------------

Blood in urine (Haematuria)	xx (xx%)
Pain passing urine (Dysuria)	xx (xx%)
Blood in semen (Haematospermia)	xx (xx%)
Temporary pain/discomfort in the perineal area	xx (xx%)
Temporary problems with erections for up to 6-8 weeks	xx (xx%)
Retention of urine requiring a temporary catheter	xx (xx%)
Prostatitis	xx (xx%)
Infection requiring admission and intravenous antibiotics	xx (xx%)
Expected risks from undergoing local anaesthetic:	xx (xx%)
Nausea and vomiting	xx (xx%)
Minor bruises for intravenous catheters	xx (xx%)
Extensive bruising, temporary hardening of vein (phlebitis) or infection	xx (xx%)
Dizziness/Vertigo	xx (xx%)
Confusion/Disorientation	xx (xx%)
Respiratory depression and apnoea	xx (xx%)
Anaphylaxis to local anaesthetic	xx (xx%)
Expected risks from undergoing general anaesthetic:	xx (xx%)
Nausea and vomiting	xx (xx%)
Dry cough	xx (xx%)
Minor bruises from intravenous catheter	xx (xx%)
Extensive bruising, temporary hardening of the vein (phlebitis) or infection	xx (xx%)
Death	xx (xx%)
Other adverse event (specify):	xx (xx%)
...	xx (xx%)
Total	xx (xx%)

**Table 1.5. 3: Listing of all new unexpected adverse events**

Subject ID	Diagnosis	Onset Date	Recovery Date	Duration (days)	Relationship	Severity	Expectedness	Serious

**Table 1.5. 4: Summary of adverse events by severity**

Total subjects (N)	Severity	No. adverse events	No. subjects AEs – n (%)	No. serious AEs	No. subjects SAEs – n(%)
	Mild	xx	xx (xx%)	xx	xx (xx%)

Imperial Clinical Trials Unit	STATISTICAL ANALYSIS PLAN	PROSTAGRAM
-------------------------------	---------------------------	------------

	Moderate	xx	xx (xx%)	xx	xx (xx%)
	...	xx	xx (xx%)	xx	xx (xx%)
	All	xx	xx (xx%)	xx	xx (xx%)

**Table 1.5. 5: Number of adverse events by causality relationship**

Subjects with AEs*						
No relationship	Unlikely	Possible	Probable	Definitely	Not Yet Defined	Total
xx	xx	xx	xx	xx	xx	xxx
Total AEs						
No relationship	Unlikely	Possible	Probable	Definitely	Not Yet Defined	Total
xx	xx	xx	xx	xx	xx	xxx

\*Table note: Where subjects have more than one AE the highest relationship has been used.

Imperial Clinical Trials Unit	STATISTICAL ANALYSIS PLAN	PROSTAGRAM
-------------------------------	---------------------------	------------

**Table 1.5. 6: Listing of all serious adverse events**

Subject ID	AE Diagnosis	Details	Relation to study	Severity	Start date	Days from baseline	Recovery date	Expectedness	Outcome	Event frequency

**Table 1.5. 7: Summary of serious adverse events by category**

Subjects with SAEs*							
Resulted in death	Life threatening	Require inpatient hospitalisation or prolongation of existing hospitalisation	Result in persistent or significant disability or incapacity	Resulted in congenital anomaly/birth defect	Other medically important event	Other	TBC
XX	XX	XX	XX	XX	XX	XX	XX
All SAEs							
Resulted in death	Life threatening	Require inpatient hospitalisation or prolongation of existing hospitalisation	Result in persistent or significant disability or incapacity	Resulted in congenital anomaly/birth defect	Other medically important event	Other	TBC
XX	XX	XX	XX	XX	XX	XX	XX

\*Table note: Where subjects have more than one SAE the highest category has been used.

Imperial Clinical Trials Unit	STATISTICAL ANALYSIS PLAN	PROSTAGRAM
-------------------------------	---------------------------	------------

**Table 1.5. 8: Number of serious adverse events by category and causality relationship**

Category	Subjects with SAEs*						
	No relationship	Unlikely	Possible	Probable	Definitely	Not Yet Defined	Total
Resulted in death	xx	xx	xx	xx	xx	xx	xx
Life-threatening	xx	xx	xx	xx	xx	xx	xx
Required inpatient hospitalisation or prolongation of existing hospitalisation	xx	xx	xx	xx	xx	xx	xx
Resulted in persistent or significant disability/incapacity	xx	xx	xx	xx	xx	xx	xx
Other medically important event	xx	xx	xx	xx	xx	xx	xx
Other	xx	xx	xx	xx	xx	xx	xx
TBC	xx	xx	xx	xx	xx	xx	xx
All SAEs							
Category	No relationship	Unlikely	Possible	Probable	Definitely	Not Yet Defined	Total
Resulted in death	xx	xx	xx	xx	xx	xx	xx
Life-threatening	xx	xx	xx	xx	xx	xx	xx
Required inpatient hospitalisation or prolongation of existing hospitalisation	xx	xx	xx	xx	xx	xx	xx
Resulted in persistent or significant disability/incapacity	xx	xx	xx	xx	xx	xx	xx
Other medically important event	xx	xx	xx	xx	xx	xx	xx
Other	xx	xx	xx	xx	xx	xx	xx
TBC	xx	xx	xx	xx	xx	xx	xx

\*Table note: Where subjects have more than one SAE, the SAE with the highest relationship has been used.

#### 11.6.6. Subgroup Analysis

**Table 1.6. 1: Output of logistic regression analysis of the probability of a screen-positive MRI result on age**

Variable	N	Odds Ratio	Standard Error	z	p-value	95% confidence interval
Age	xxx	x.xx	xx.xx	x.xx	x.xxx	x.xx to x.xx
Intercept	xxx	x.xx	xx.xx	x.xx	x.xxx	x.xx to x.xx

Logistic regression model: MRI screening result = intercept + age

Repeat analysis for both screen-positive MRI cut-offs defined by PIRADS scoring system in Section 10.3.1

**Table 1.6. 2: Output of logistic regression analysis of the probability of a screen-positive ultrasound result on age**

See output in Table 1.6. 1, but for screen-positive ultrasound results.

Logistic regression model: ultrasound screening result = intercept + age

Repeat analysis for both screen-positive ultrasound cut-offs defined by US scoring system in Section 10.3.2

**Table 1.6. 3: Output of ordinal regression analysis of PIRADS score on age**

Variable	N	Cumulative Odds Ratio	Standard Error	z	p-value	95% confidence interval
Age	xxx	x.xx	xx.xx	x.xx	x.xxx	x.xx to x.xx
Intercept	xxx	x.xx	xx.xx	x.xx	x.xxx	x.xx to x.xx

Proportional odds model: PIRADS score = intercept + age

See Section 10.3.1.

**Table 1.6. 4: Output of ordinal regression analysis of US score on age**

See output in Table 1.6. 3, but for US score.

Proportional odds model: US score = intercept + age

See Section 10.3.2.

### 11.6.7. Interobserver Agreement for MRI

**Table 1.7. 1: Agreement in PIRADS score for MRI scans between local reader and central reader, and Cohen's Kappa statistic**

		Central reader					
		1	2	3	4	5	Total
Local reader	1	xxx	xxx	xxx	xxx	xxx	xxx
	2	xxx	xxx	xxx	xxx	xxx	xxx
	3	xxx	xxx	xxx	xxx	xxx	xxx
	4	xxx	xxx	xxx	xxx	xxx	xxx
	5	xxx	xxx	xxx	xxx	xxx	xxx
	Total	xxx	xxx	xxx	xxx	xxx	xxx

Agreement (%)	Expected agreement (%)	Kappa statistic	Standard error	95% confidence interval	Z	Pr > Z
xx.xx%	xx.xx%	x.xxx	x.xxx	x.xx to x.xx	x.xxx	x.xxx

Red indicates agreement between PIRADS scores

Green shading indicates concordant scores, where management decision to perform biopsy would not have changed. Blue shading indicates discordant scores, where management decision to perform biopsy would have changed.

See Section 10.3.1

Imperial Clinical Trials Unit	STATISTICAL ANALYSIS PLAN	PROSTAGRAM
-------------------------------	---------------------------	------------

## 11.7. Figures to Present

### 11.7.1. Other Test Performance (MRI and US) End Points

- Histogram to present the distribution of men across discrete values of Likert score (MRI scoring system)
- Histogram to present the distribution of men across discrete values of PIRADS (MRI scoring system)
- Histogram to present the distribution of men across discrete values of ultrasound score (US)
- Histogram to present distribution of the type of cancer detected across discrete values of Likert score (MRI scoring system) (repeated for each of the thresholds defined in Section 8.1 separately)
- Histogram to present distribution of the type of cancer detected across discrete values of PIRADS (MRI scoring system) (repeated for each of the thresholds defined in Section 8.1 separately)
- Histogram to present distribution of the type of cancer detected across discrete values of ultrasound score (US) (repeated for each of the thresholds defined in Section 8.1 separately)
- Graph displaying proportions of results for MRI compared to histology results for detection of clinically significant cancer
- Graph displaying proportions of results for ultrasound compared to histology results for detection of clinically significant cancer
- Graph displaying proportions of results for PSA compared to histology results for detection of clinically significant cancer.

### 11.7.2. Feasibility End Point

- Bar charts displaying the proportions of participants who selected each Likert score, compared between screening tests (PSA, ultrasound and MRI), for each EBQ component (embarrassment, pain, burden, anxiety) (10)
- Bar charts displaying the proportions of participants who selected each Likert score, compared between screening tests (PSA, ultrasound and MRI), for each PBQ component (embarrassment, pain, burden, anxiety, repeat test recommendation) (10).

### 11.7.3. Subgroup Analysis

- Boxplots to present distribution of age over screen-positive and negative MRI results (repeated using both PIRADS cut-offs in Section 10.3.1)
- Boxplots to present distribution of age over screen-positive and negative ultrasound results (repeated using both US cut-offs in Section 10.3.2)
- Boxplots to present distribution of age across PIRADS scores
- Boxplots to present distribution of age across US scores

## 12. Missing Data

Follow up time will be calculated as the time from enrollment. As the period of follow-up is relatively short, there should be minimal problems with loss to follow-up in this study. Circumstances and reasons why a patient is lost to follow-up will be summarised using the CONSORT diagram, and characteristics of patients with missing data or those lost to follow up will be described. Given the thorough nature of our follow-up procedure we expect the issue of missing data to be relatively minimal and therefore it is unlikely that imputation of data will be required.

Imperial Clinical Trials Unit	STATISTICAL ANALYSIS PLAN	PROSTAGRAM
-------------------------------	---------------------------	------------

### 12.1. Missing Questionnaire Responses

Every effort should be made by the clinical team to ensure questionnaires are completed in full. If this is not possible, missing values may be present in patient responses to these questionnaires.

Patients with missing item responses for EBQ and PBQ will be excluded from the final analysis, as an overall questionnaire score cannot be computed for these patients.

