### 10.2. Combined Questionnaire Scores

Overall (combined) and component (question) scores for each patient at each visit, for the following questionnaires, are required as part of the feasibility end point analysis:

- EBQ (for each screening test) (Visit 1)
- PBQ (for each screening test) (Visit 1).

Imperial Clinical Trials Unit	STATISTICAL ANALYSIS PLAN	PROSTAGRAM
-------------------------------	---------------------------	------------

Details of the questionnaires are included in Appendix 1.

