Assess the acceptability of each diagnostic test measured with EBQ, PBQ and time taken to complete each screening test	
 
EBQ and PBQ Questionnaires (see Appendix 1 for details):             
 
Summary statistics for overall scores for EBQ and PBQ, for each screening test                 
 
Paired t-tests comparing mean overall scores between pairs of screening tests (MRI & PSA, MRI & ultrasound, ultrasound & PSA), for EBQ and PBQ separately
 
Paired t-tests comparing mean difference between pre- and post-screening test scores, for each screening test
 
 
 
Proportions within each value of the Likert score, for each EBQ component, for each screening test (Appendix 1)
 
Mean score for each EBQ component, for each screening test                 
 
Paired t-tests comparing mean component scores between pairs of screening tests (MRI & PSA, MRI & ultrasound, ultrasound & PSA)
 
 
 
Proportions within each value of the Likert score, for each PBQ component, for each screening test (Appendix 1)
 
Mean score for each PBQ component, for each screening test                 
 
Paired t-tests comparing mean component scores between pairs of screening tests (MRI & PSA, MRI & ultrasound, ultrasound & PSA)
 
 
 
 
 
	Participants who completed the relevant test for the respective analyses   For the paired tests, participants who completed both tests in each pair

Imperial Clinical Trials Unit	STATISTICAL ANALYSIS PLAN	PROSTAGRAM
-------------------------------	---------------------------	------------

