#### 11.2.4. Feasibility End Point Analysis

Summary statistics will be presented for the overall (combined) EBQ and PBQ scores for each screening test. The overall scores will be calculated using the method described in Appendix 1. Paired t-tests will be conducted to compare the mean overall scores between pairs of screening tests (MRI & PSA, MRI & ultrasound, and ultrasound & PSA), for EBQ and PBQ scores separately. Pre-screening test scores are measured using the EBQ, and post-screening test scores are measured using the PBQ. Paired t-tests will also be used to compare the mean difference between pre- and post-screening test scores, for each screening test separately.

Each component of EBQ and PBQ is represented by a single question. EBQ has a total of four components (four questions), and PBQ has a total of five components (five questions) (see Appendix 1 for further details). Both EBQ and PBQ share four common components (embarrassment, pain, burden, anxiety).

Summary statistics will be presented for the separate components for the EBQ. These will be reported as the proportions within each value of the Likert score, for each EBQ component, measured for each screening test (PSA, ultrasound and MRI). The mean scores of each EBQ component, measured for each screening test (PSA, ultrasound and MRI) will also be calculated and reported. Paired t-tests will compare the mean EBQ component scores between pairs of screening tests (MRI & PSA, MRI & ultrasound, and ultrasound & PSA). A similar analysis will be conducted for the PBQ component scores.

Paired t-tests will compare the mean difference between pre- and post-screening test scores, for each common component of EBQ and PBQ (embarrassment, pain, burden and anxiety).

The proportions of preference for each screening test, as measured by EBQ (“Expected preference”) and PBQ (“Final preference”) separately, will be reported.

Further analysis will be conducted on screening test preference, as measured by PBQ, after the screening tests. Screening test preference will be dichotomised in four ways, as outlined in Section 10.3.9. A multivariable logistic regression model will be fit to each of these newly generated dichotomous variables, separately, controlling for pre-specified baseline patient factors. If any of the factors have more than 10% missing data then we will not include the factor in the multivariable logistic regression. The number of pre-specified baseline patient factors to be included in the

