#### 20.1.3. EBQ and PBQ

The Expected Burden Questionnaire (EBQ) and Perceived Burden Questionnaire (PBQ) have been developed for use in bowel cancer screening. It has been used in studies investigating the acceptance of CT Colonography/FOBT (10) and has been adapted for the tests used in this study.

EBQ is comprised of four questions addressing the expected extent of embarrassment, pain, burden and anxiety caused by each test. This is followed up by a question summarising which test the patient expects to prefer. The EBQ is completed at visit 1, before the screening tests. The

Imperial Clinical Trials Unit	STATISTICAL ANALYSIS PLAN	PROSTAGRAM
-------------------------------	---------------------------	------------

responses to the first four questions are coded as a 5-point Likert score, 1 = not at all, 2 = slightly, 3 = somewhat, 4 = rather and 5 = extremely (14). Each question, representing each component, will be reported separately. An overall burden score will also be calculated for each screening test by summing the response scores to the first four questions. Lower overall scores represent lower expected overall burden for that particular screening test.

Similarly, PBQ is comprised of five questions addressing the embarrassment, pain, burden and anxiety experienced from each test, and how likely the patient is to have the test again, if recommended. This is followed up by a question summarising which test the patient preferred. The PBQ is completed at visit 1, after each screening test. The responses to the first five questions will be coded as 1 = not at all, 2 = slightly, 3 = somewhat, 4 = rather and 5 = extremely (14). Each question, representing each component, will be reported separately. An overall burden score will be calculated for each screening test by summing the response scores to the first four questions, excluding the question relating to repeat test recommendation. Lower overall scores represent lower perceived overall burden for that particular screening test.

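### Read literally, SAP 12.1 drops a man with any missing EBQ or PBQ item from the whole acceptability analysis, for a reason that covers only the summed score

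*SAP*

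**What the plan says.** SAP 12.1 (Missing Questionnaire Responses) says that "Patients with missing item responses for EBQ and PBQ will be excluded from the final analysis", and gives one reason: "as an overall questionnaire score cannot be computed for these patients". It does not define the final analysis or limit the exclusion to a test, a questionnaire or a type of analysis.

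Other sections describe how the questionnaires are used:

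- SAP 11.2.4 (Feasibility End Point Analysis) says "Each component of EBQ and PBQ is represented by a single question". The EBQ has four such questions and the PBQ five, asked for MRI, ultrasound and PSA.
- SAP 20.1.3 (Appendix 1) says "Each question, representing each component, will be reported separately". The overall score for each test is the sum of the first four items. For the PBQ this means "excluding the question relating to repeat test recommendation".
- SAP Table 1, feasibility rows, sets the population as men who completed the relevant test and adds "For the paired tests, participants who completed both tests in each pair". It does not ask for a complete questionnaire.
- SAP 11.2.4 gives the preference regression its own missing-data rule: a factor with more than 10% missing is left out. The EBQ items are factors 12 to 15 in its ranked list.
- SAP 12 expects few missing data, thinks imputation unlikely, and plans to describe men with missing data. No sensitivity analysis is specified for the exclusion in 12.1.

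**The concern.** The rule is wider than its reason. The reason is a property of one summed score, for one test on one questionnaire. The rule removes a person.

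Most of the planned acceptability work needs no summed score. The component proportions, component means, component t-tests between tests and before/after, and the preference proportions each use one or two items. The preference regression uses the preference answer and baseline factors.

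At stake is the acceptability comparison of MRI, ultrasound and PSA, which the primary outcome paper will report. If the sentence is applied as written, usable answers are thrown away. If men who leave items blank differ from those who do not in how acceptable they find a test, the men retained are a selected group. The wording also leaves room for two analysts to reach different numbers from the same data.

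**Working it through.** **Does the stated reason apply? Analysis by analysis (SAP Table 1, 11.2.4, 20.1.3)**

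| Analysis | Items needed | Needs the summed score? |
|---|---|---|
| Overall score, one test, one questionnaire | first 4 | yes |
| Overall scores compared between two tests, or EBQ to PBQ for one test | 8 | yes |
| Component proportions and means | 1 | no |
| Component compared between two tests, or EBQ to PBQ | 2 | no |
| Preference proportions | the preference question | no |
| Preference regression | PBQ preference plus the factors included | no |

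The reason holds for the first two rows only. Within those rows it fails for a man whose only gap is the fifth PBQ item, because all his scores can be computed. It also fails for the MRI and PSA scores of a man whose only gap is on ultrasound, because scores are formed test by test.

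**Base number.** The documents give no figure for item missingness, so the planned sample size serves as the base. By the SAP Section 6 formula, n = 1.96² × 0.611 × 0.389 / 0.05² = 365.2, so 366, as stated. With 10% dropout, 366 / 0.9 = 406.7; the SAP states 406, which is used below.

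**Item count.** (4 EBQ + 5 PBQ) × 3 tests = 27 items per man, besides the preference questions.

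**Illustrative loss.** Let q be the chance that an item is missing. The values of q are assumed, and items are first taken as independent. The share kept when k items must all be present is (1 − q)^k. Men kept out of 406, with the share lost in brackets:

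| Items that must be complete | q = 0.5% | q = 1% | q = 2% |
|---|---|---|---|
| k = 2, paired component comparison | 402.0 (1.0%) | 397.9 (2.0%) | 389.9 (4.0%) |
| k = 4, one overall score | 397.9 (2.0%) | 390.0 (3.9%) | 374.5 (7.8%) |
| k = 8, paired overall-score comparison | 390.0 (3.9%) | 374.6 (7.7%) | 345.4 (14.9%) |
| k = 27, the literal rule | 354.6 (12.7%) | 309.5 (23.8%) | 235.3 (42.0%) |

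For example, at q = 1% the literal rule gives 0.99^27 = 0.762, and 0.762 × 406 is about 310 men. A two-item comparison on available cases gives 0.99² = 0.980, or about 398.

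**Sensitivity to independence.** If the gaps all fall in the same men, the share lost under the literal rule drops towards q itself, that is 0.5% to 2%. The last row of the table is therefore the unfavourable end of a wide range.

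**The case against.** The strongest reply is that the sentence in 12.1 should be read with its reason clause. On that reading the excluded men leave only the overall-score analyses. Score-by-test definitions, the per-test populations in Table 1 and the separate N on each row of the paired-test shells all fit this. The sentence could even be taken to mean men with gaps on both questionnaires. Both questionnaires are completed at visit 1, the clinical team is asked to secure full completion, and few gaps are expected. Much of this stands: the score-level reading is possible and the loss would then be small. It does not remove the point, because the text does not say so, and the repeat-test item contradicts the stated reason on any reading.

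A reader might infer more than the documents support:

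- **That the comparison is biased towards compliant men.** Nothing links a blank item to dislike of a test, and not having a test is a different event from leaving an item blank. Selection is a risk of unknown direction.
- **That 12.1 contradicts Table 1.** Table 1 sets populations and 12.1 may act within them. The two are unreconciled, which is less than a contradiction.
- **That up to 42% of men will be lost.** This needs the widest reading, a 2% item rate and independent items, none of which the documents establish.
- **That the primary result is affected.** Its population is men with MRI results, and nothing ties that to the questionnaires.

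**Conclusion.** The point holds for the acceptability end point. As worded, 12.1 excludes the man although its reason reaches only the score that cannot be formed, and for the PBQ repeat-test item the reason is untrue. Usable component, pre/post and preference data would be lost, with possible selection.

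The size is conditional. If all 27 items must be complete and gaps are independent, assumed item rates of 0.5% to 2% lose about 13% to 42% of men. If exclusion applies to one four-item score, the same rates lose about 2% to 8%. If gaps cluster in the same men, the literal rule loses little more than the item rate. The case for changing the text rests on the mismatch between rule and reason, which needs no assumed rate. If the sponsor meant score-level exclusion, the text should say so; if it meant the literal rule, the reason given does not justify it.

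**What to change.** Replace the exclusion sentence in SAP 12.1 with wording such as:

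*A man missing any of the first four items of a questionnaire for a test is excluded only from overall-score analyses that need that score. Component, pre/post and preference analyses use all men with the items involved, within the Table 1 populations.*

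Report N for each analysis. The paired-test shells already carry it; add it to Tables 1.3.1, 1.3.5, 1.3.8, 1.3.11 and 1.3.12, which do not.

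The cost is a short SAP amendment and some shell edits, with no new data or visits. The downside is that N will differ slightly between analyses, so rows will not all describe exactly the same men.
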